8.52 Study Safety Monitoring

Since Phase I and Phase II studies are not routinely reviewed by a Data and Safety Monitoring Board (DSMB), it is the responsibility of the Protocol Team to interpret safety data, and make decisions regarding SADRs that are needed to protect subjects from undue risk. In addition, the Study Monitoring Committee described above is appointed to provide impartial reviews in situations where patient safety is in question.

For safety monitoring, a drug related SAE is an SAE that is judged to be “definitely”, “probably” or “possibly related” to study drug (ETR).

The safety and tolerability of the study agent will be monitored by means of adverse events reports and toxicity reports presenting laboratory and clinical events. It is required that the data required for the toxicity reports be entered into the database within 48 hours of the time at which the results of the laboratory tests or clinical examinations become available.

Reports compiled by the Data Management Center (DMC) will be reviewed and discussed by the Protocol Team on conference calls held at least twice a month during the dose-finding stage and every month thereafter and by the study’s Study Monitoring Committee under conditions specified above. Data on accrual, pharmacokinetics and toxicity will be reviewed.

Adverse events will be monitored from screening onwards throughout the follow-up period. If the protocol team identifies any potentially treatment-related toxicities, which may compromise subject safety, the study will be paused and the Study Monitoring Committee will review all relevant data and will determine whether, and under what conditions, the study would be allowed to proceed.

8.521 Rules for Suspending Accrual to Assess Safety Following an Adverse Event

Accrual will be temporarily suspended if any subject has a life threatening Suspected Adverse Drug Reaction (SADR), or death, or any Grade 4 event that may not be judged to be life- threatening but is judged to be probably or definitely attributable to the study medication.

Following temporary suspension of accrual, the Study Monitoring Committee will be convened and will further review the safety data within 48 hours of notification of the event to determine if continuation of accrual is appropriate. If the Study Monitoring Committee agrees that the study drug is likely to be safe for additional subjects, they may allow accrual to resume. Regulatory agencies will be notified of the event and the team’s decision after this review of the safety data has taken place.

8.522 Accrual Rate Evaluation

Accrual to this study will be monitored by the IMPAACT leadership in accordance with standard operating procedures. The team will monitor feasibility quarterly, first based on site registration and then on accrual. Initially, the team will monitor site registration monthly to ensure that an adequate number of sites have registered to complete the protocol. If relatively few of the eligible sites have registered after the protocol has been approved for 6 months, the team will re- assess the feasibility of the protocol and the reasons why sites have not registered, and may amend the protocol accordingly. Once one-third of eligible sites have registered, the team will assess accrual on a quarterly basis. If any cohort during the dose-finding stage has

not accrued half its subjects within 6 months of opening, the team will identify the reasons for lack of accrual and possibly amend the protocol accordingly.

A trial go/no-go decision point will be set approximately 2 years after opening of Cohort 2. At that time, an analysis across all age cohorts (irrespective of the number of enrolled subjects or length of follow-up within each age group and across the age groups) will be performed, for the purpose of complying with regulatory requirements for Janssen R&D. In addition, accrual rate and all of the relevant safety and pharmacokinetic data will be examined to determine whether it is safe and worth to continue the trial in an attempt to find an optimal dose for Cohorts II and III.

8.523 Long Term Follow-Up for Safety

Subjects who successfully complete 48 weeks of ETR treatment will be followed for clinical long term safety follow up every 12 weeks. Sites should refer to Section 5.5 and Appendix IE.

8.6 Analyses

8.61 Summary of Dose Finding Data

The analysis of dose finding data will consist of descriptive statistics summarizing the safety and PK data from the dose finding phase of the study. (See Section 9.0 for PK analysis). The safety data will be analyzed by cohort and will present the results of the safety evaluations applied to each starting dose regimen tested within each cohort, including information indicating which starting doses have passed or failed the safety guidelines. For each starting dose within each cohort, every adverse event of Grade 3 or higher will be listed, along with subject demographics, the dose prescribed to the patient at the time of the event and the protocol team's assessment of the probability that this event was due to the study treatment (not related, probably not related, possibly related, probably related or definitely related).

8.62 Analysis of Data Representing Exposure to the Doses Judged to be Optimal for Each Cohort

These analyses will be stratified by cohort. The findings will be presented in both in aggregate and broken down by cohort, with estimates bounded by 95% confidence limits. Given that the small sample sizes within cohorts will provide limited power for statistical tests of differences across age cohorts, interpretation of the results will depend upon whether differences across cohorts are great enough to be considered to be clinically significant. If no such differences are observed, then the clearest interpretation of the findings will come from the aggregated data, where analyses will have the greatest statistical precision. However, if results vary across cohorts to a clinically important extent, interpretation of results should take into account the issues represented by the stratification factor.

8.63 Primary Analyses - performed on data through the Week 24 and Week 48 visit

8.631 Safety

The primary safety analysis will include only subjects whose total exposure to ETR has been at the dose judged to be optimal for their cohorts. Subjects whose doses have been adjusted for inadequate PK will be excluded. Subjects who have been removed from treatment or have had their doses reduced due to toxicities while on the optimal dose will be included and treated as safety failures in the primary safety

analysis. Additional analyses will look at the combined data from subjects whose doses failed and those who have been treated solely at the optimal doses determined for their cohorts and without individual PK determined dose adjustments. Sensitivity analyses will be performed to determine whether the exclusion of subjects whose doses have been adjusted creates a selection bias which impacts upon any results.

Each subject's safety data will be summarized as: the worst grade of adverse event experienced during the first 24 weeks (and 48 weeks) of exposure to the optimal dose of the study treatment and the worst grade of adverse event judged to be at least possibly related to study treatment during this time period. Frequency distributions of these safety outcomes will be presented in the aggregate and broken down by age. Listings of all Grade 3+ events will be provided, broken down by type of toxicity (hepatic, hematologic etc.).

The proportions of subjects experiencing Grade 3+ adverse events will be presented in aggregate and broken down by age cohort, with these proportions bounded by exact 95% confidence intervals. Similar analyses will present the proportions of subjects exhibiting Grade 3+ events which have been judged to be at least possibly related to study medication, again bounded by exact 95% confidence intervals.

8.632 Key Secondary Analyses

8.6321 Viral Load

Virologic outcomes, based on HIV-1 RNA (copies/ml), will be assessed at weeks 8, 12, 24 and 48. The criteria for success are: at least a 0.5 log₁₀ reduction in HIV-1 RNA (copies/ml) at week 8, at least a 1 log₁₀ reduction in HIV-1 RNA (copies/ml) at week 12 and either HIV-1 RNA ≤ 400 copies/ml or at least a 2 log reduction in HIV-1 RNA at weeks 24 and 48.

For regulatory submissions, at each of these time points the primary definition of virologic outcome will be calculated according to a Missing, Switch or Discontinuation = Failure (MSDF) algorithm – as codified by the FDA's snapshot algorithm. Subjects may be classified as virologic failures if they have missing HIV-1 RNA data throughout the window surrounding the time point of interest. (This window and related details will be defined in the analysis plan.) In addition subjects will be classified as virologic failures at any of these time points if they meet any of the following conditions prior to that time point:

- a) Discontinuation of study treatment due to reasons other than AE or death and viral load was > 400 copies/mL at last available visit.
- b) Change in background therapy not allowed in the protocol.
- c) Change in background ART substitutions permitted per protocol unless the decision to switch is documented as being before or at the first on-treatment visit where HIV-1 RNA is assessed (Week 4).

Subjects who only discontinued a background ARV or who had formula substitutions (substituting single agents for fixed dose combinations and vice versa of the same ARV) in their OBT are not considered as having OBT changes and will not be analyzed as virologic failures. Otherwise, virologic success will be defined as having HIV-1 RNA ≤ 400 copies/mL by the last available HIV-1 RNA assessment while the subject is on-treatment within the visit of interest window. The proportions of subjects meeting the criteria for virologic success at each of these time points will be bounded by exact 95% confidence intervals, and will be presented both in the aggregate and broken down by age cohort.

Table 9 presents exact 95% confidence intervals around various potential rates of virologic success which might be observed in a total sample of 36 subjects or in subsamples of various sizes (N = 12, 24).

Table 9. Percent of Subjects Meeting Criterion for Virologic Success with Exact 95% Confidence Intervals

N	No. of Subjects (%) with Undetectable RNA	95% C.I.
12	1 (8%)	0.2% -- 38%
24	2 (8%)	1% -- 27%
36	4 (11%)	3% -- 26%
12	3 (25%)	5% -- 57%
24	6 (25%)	10% -- 47%
36	9 (25%)	12% -- 42%
12	6 (50%)	21% -- 79%
24	12 (50%)	29% -- 71%
36	18 (50%)	33% -- 67%
12	9 (75%)	43% -- 95%
24	18 (75%)	53% -- 90%
36	27 (75%)	58% -- 88%
12	11 (92%)	62% -- 99.8%
24	22 (92%)	73% -- 99%
36	33 (92%)	78% -- 98%

8.6322 CD4 Response

Change from baseline to weeks 24 and 48 in CD4 count, CD4 percent and CD4/CD8 ratio and percent will be bounded by 95% confidence intervals and presented both in the aggregate and by age cohort. In addition, the proportions of subjects exhibiting an absolute drop of > 5% in CD4 percent from baseline to weeks 12, 24 and 48 will be presented, bounded by 95% confidence intervals. Subjects who meet any of the conditions (a) to (c) of Section 8.6321 or who have absolute drop of > 5% in their CD4% will be considered as treatment failures in these analyses.

8.6323 HIV Drug Resistance

Correlations between baseline HIV genotypic and phenotypic drug resistance and any subsequent virologic failure will be evaluated. Subjects will be assessed for HIV genotypic and phenotypic drug resistance to the OBT and ETR at screening, at the time of virologic failure (if this occurs) and at early discontinuation.

8.6324 Additional Interim Analyses for Regulatory Purposes

To comply with regulatory requirements, additional interim analyses of data from Cohort 1 will be performed when at least 12 evaluable subjects have reached Week 24 and Week 48. Also to address regulatory expectations, an additional analysis across all age cohorts will be performed through Week 48 on at least 18 subjects. These analyses will be performed by Janssen R&D and will focus primarily on safety data, presented as described in Section 8.631 and pharmacokinetic data, presented as described in Section 9.0. A secondary analysis of virologic success, as described in Section 8.6321 will also be presented. These analyses will be shared with the P1090 Team.

8.633 Exploratory Analyses

8.6331 CYP Gene Profiles

Descriptive analyses will examine the association between pharmacokinetic parameters of ETR and subject-specific CYP gene profiles.

9.0 CLINICAL PHARMACOLOGY PLAN

9.1 Pharmacology Objectives

The clinical pharmacology studies are designed to determine the steady-state pharmacokinetic (PK) profile and dosing schedule of orally administered etravirine (ETR) in HIV-1-infected children \geq 2 months to < 6 years of age. ETR PK and dose requirements will be determined when given with other ARV agents. All subjects (in the mini cohort and then the full cohort for that age) will need to undergo an initial 12 hour intensive PK study on day 14 (± 4 days) of study drug administration.

9.2 Primary and Secondary Data

Primary: AUC_{12h}

Secondary: C_{max} , C_{12hr} , T_{max} , CL/F , $T_{1/2}$, Vd and PK parameters (C_{max} and C_{12hr}) by CYP2C9 and CYP2C19 genotype

9.3 Study Design, Modeling and Data Analysis

9.31 PK Criteria

For this study, the area under the plasma concentration-time curve over 12 hours (AUC_{12h}) of ETR, as determined following an observed dose under fed, steady-state conditions will be the PK parameter for determination of the acceptability of the ETR dose, and any individual subject dose adjustments. The target geometric mean ETR AUC_{12h} for this study is between 60% and 150% of the geometric mean AUC_{12h} observed in HIV-1-infected treatment-experienced adults from the DUET studies (i.e. between 2713 and 6783 ng•h/mL). For the individual subject management in this study, subjects with an individual AUC_{12h} below the 10th percentile of adult exposure (i.e. < 2350 ng•h/mL) will be dose-adjusted in order to meet an $AUC_{12h} \geq 2350$ ng•h/mL.

No apparent pharmacodynamic relationship for ETR has been identified in adults, implying that the plasma concentrations achieved (in the DUET studies) were, largely, on the flat portion of the expected sigmoid exposure-response relationship. The threshold AUC_{12h} value of < 2350 ng•h/mL representing the 10th percentile of AUC in adults was selected, with the objective of achieving a distribution for ETR AUC_{12h} values in children that approximates that in HIV- infected adults who received ETR 200 mg twice daily (in combination with darunavir/ritonavir). While the ETR AUC_{12h} will be the primary PK parameter for acceptability of dose determination, the P1090 core protocol team will also consider the C_{12h} of ETR in their evaluation.

9.32 Starting Dose

The starting dose for ETR in cohort I (≥ 2 years to < 6 years of age) was 5.2 mg/kg twice daily. This dose was based on the results of the analysis of trial TMC125-C213 (see Section 1.32). Based on the safety profile of ETR, the concern for under-dosing in children (25) (26) (27) (28) and the usual need for slightly higher C_{max} in children to achieve comparable trough concentrations (due to a faster apparent oral clearance) the initial starting dose of 5.2 mg/kg twice daily reflected an appropriate balance of these considerations based on available data at that time.

An evaluation of the PK data from the first 6 children enrolled in Cohort I of P1090 indicated that the geometric mean etravirine exposure (at the 5.2mg/kg BID dose for the whole cohort) was lower than expected, and the chance of meeting the required geometric mean etravirine AUC_{12h} (comparable to adults) for the full cohort was very low (see also section 1.32).

All available etravirine PK data in pediatric subjects, including the P1090 subjects, were used in a modeling and simulation approach to better inform the choice of a revised starting dose for ETR for Cohort I and the starting dose for other cohorts in this study. It was also decided that, instead of a mg/kg dose across all ages, it would be more appropriate to develop dosing based on weight bands. The starting doses for Cohorts II and III are also informed and chosen by the results of Cohort I, as detailed in Section 8.1. For example, after evaluation of the first 6 subjects of Cohort I and criteria were met, Cohort I re-opened to accrual of additional subjects to complete the full cohort. Opening of Cohort II to accrue the first mini-cohorts of 6 subjects was done based on the assessment by the protocol team that sufficient data (PK and safety) were available to appropriately inform the choice of starting dose regimen for this cohort. The same applies for opening of Cohort III. Within Cohort III, subjects below 6 months of age will only be enrolled upon availability of initial safety and PK data from subjects between 6 months and 1 year of age. Appendix III gives the tables for the revised starting dose for Cohort I, starting doses for Cohort II and III and guidelines about re-evaluating the dose regimen if warranted based on the PK data.

9.33 Intensive PK Evaluations

All subjects will undergo an intensive PK study. This PK evaluation will be conducted on day 14 (± 4 days). Subjects should have taken their ETR doses as directed by the study physician, for 7 days prior to the intensive PK visit, without any missed doses. Sites are encouraged to call the subjects family, the day before the intensive PK visit, so that the site staff can confirm that the subject has not missed any doses in the previous 7 days.

If the subject has missed a dose, the intensive PK visit should be rescheduled to occur 7- 14 days after the last missed dose. The site is again encouraged to call the subjects family the day before the rescheduled intensive PK Visit so the staff can confirm the subject has not missed any doses in the previous 7 days. If the subject has missed a dose, the PK visit will be cancelled, and the subject will be withdrawn from the study.

The intensive PK visit should be scheduled so that a witnessed dose of ETR is taken within a range of 11 to 13 hours after their previous dose. Once the subject has arrived at the clinic, he/she should be offered a meal appropriate for age. The team suggests that a heparin lock be used for the intensive PK visit if at all possible. The PK dose of medication should be administered within 30 minutes following the start of the meal. If the subject vomits within 15 minutes of taking their medication, the dose should be re-

administered. Re-dosing is not allowed if the subject vomits more than 15 minutes after study medication intake. In the event that the subject vomits more than 15 minutes after study medication intake on the day of pharmacokinetic evaluation, that assessment must be rescheduled. Subjects may resume food intake 2 hours after their dose of ETR at the intensive PK visit.

The intensive PK evaluation will consist of obtaining a pre-dose plasma concentration, and following an observed dose, post dose plasma concentrations at 1, 2, 4, 6, 9 and 12 hours. To allow for some flexibility, the 9-hour sample can be collected within a window of 8 to 10 hours post-dose and the 12-hour sample within a window of 11 to 13 hours post-dose. If necessary, the sample 1 hour post-dose and/or 9 hours post-dose can be deleted to reduce the amount of total blood drawn from 7 samples over 12 hours to 5 or 6 samples, over 12 hours. ETR plasma concentrations will be determined in “real time” in a CLIA-certified IMPAACT pharmacology laboratory. The goal is for ETR plasma concentration information to be available for individual and cohort dose evaluation within 2 weeks, or at study week 4.

If the protocol team believes the intensive PK was conducted incorrectly or the results inaccurate, subjects may be asked to repeat an intensive PK visit on the same dose.

For the intensive PK evaluations of ETR, the primary PK parameter will be AUC_{12h} . Other secondary parameters that will be calculated include CL/F , $Vd, T_{1/2}$, C_{max} , C_{12h} and T_{max} . Plasma concentration-time data will be graphically inspected, and standard non-compartmental techniques will be used to assess PK parameters. C_{max} and C_{12h} will be taken as the maximum and 12 hour observed concentration, respectively, and T_{max} is the time at which C_{max} occurs. The AUC_{12h} will be determined using the linear-linear trapezoidal rule. CL/F will be calculated as dose/ AUC_{12h} . The terminal elimination half-life is also a secondary parameter and will be determined using regression analysis on a minimum of 3 points (not including C_{max}) in the terminal elimination phase when possible.

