6.6 Concerns Regarding Non-Adherence

In the rare event where the results of a single subject's intensive PK are extremely low, AND the site clinician/protocol team strongly suspect non-adherence, an additional subject may be enrolled into the mini-cohort to replace the non-adherent subject. The non-adherent subject may remain on study and on study drug (ETR) but will not be considered for dose-finding or safety final analysis.

Medication adherence is critical to successful antiretroviral therapy. In addition to compromising the efficacy of the current regimen, suboptimal adherence has implications for limiting future effective regimens for subjects with resistant strains.

Evidence indicates that adherence problems occur frequently in children. Studies have reported that fewer than 50% of children and/or their caretakers reported full adherence to the regimens. Although a variety of factors have been associated with adherence, no clear predictors of either good or poor adherence have been consistently identified in children.

As a part of this trial, adherence to therapy should be stressed at each visit, along with continued exploration of strategies to maintain and/or improve adherence.

Multiple methods of determining adherence to ARV therapy will be used simultaneously (e.g., quantitative self-report, pill counts). Pill counts will take place at each visit and will be recorded on the drug accountability form. Adherence to the study drug, OBR, and assessment of the palatability of the study drug, will also be monitored in the form of questionnaires/CRF administered by the site staff.

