The overall safety and PK data of the first 6 subjects on a given cohort will be evaluated with respect to the guidelines specified in Section 8.512 and in Section 9.0 of the protocol. Once these subjects have passed both PK and safety criteria, 6 additional subjects will be accrued to complete each cohort (up to 12 additional subjects may be accrued to Cohort I). The full cohort must also pass the PK and safety criteria (see Section 8.513 and Section 9.0). If the mini or full cohort fails either the safety or the PK guidelines, then the starting dose will be adjusted in the appropriate direction, (upwards for inadequate PK values; downwards for safety failure), if this is feasible. Subjects in a cohort that failed PK or safety but were receiving the same dose as that recommended in the new dosing cohort will be included in PK and safety analysis of the new dose and additional new subjects will be enrolled as appropriate at the new dose in order to have a mini-cohort of 6 subjects treated with the new dose. An initial evaluation of safety and PK will be made on the basis of data from these subjects. The evaluation will proceed as described above. In the event that the mini- or full cohort fails the PK criteria before the cohort completes accrual, then safety will be evaluated on all available subjects to confirm that a dose increase is not contraindicated.

If the P1090 core protocol team judges a given subject's PK data to be unevaluable, the subject will be replaced for dose finding purposes. Note that the subject would be replaced for evaluating safety, as well as PK, criteria, since unevaluable PK data would reflect uncertainty about appropriate exposure to the study medication.

The study accrual is designed to yield at least 36 evaluable subjects for the Week 24 (and 48) safety analyses, which analyses will occur when the last subject of the last cohort has reached week 24 (or Week 48). For these safety analyses, "evaluable" will be defined as having been treated exclusively on the dose determined to be optimal for a given age cohort and having either completed 24 (or 48) weeks of exposure to the study drug or having been classified as a safety failure, due to a study drug related adverse event

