14. Wherever possible, the CYP genotyping and viral load PCR can be run from the same blood sample. The blood draw should be collected and spun down to isolate pellets for PBMCs (for CYP genotyping) and the plasma can be used for the viral load. Otherwise, a separate blood tube should be drawn.
15. Sites should also perform the palatability assessment at these visits.
16. Subjects must have taken their ETR doses as directed by the study physician, for 7 days prior to the intensive PK visit, without any missed doses. Sites are strongly encouraged to call the subject, the day before the intensive PK visit, so that the site staff can confirm that the subject has not missed any doses in the previous 7 days. If the subject has missed a dose, the PK visit must be re-scheduled within the Day 14 (\pm 4 days) window.
17. The ECG at the intensive PK visit should be collected following the 4 hour blood draw. This time point is generally when the drug level is at its highest.
18. At weeks 4 and 24, one sample should be timed to fall within a window of 1 to 4 hours following a dose of etravirine.
19. At week 8, one sample should be timed to fall within a window of 4 to 8 hours following a dose of etravirine.
20. At weeks 12 and 48, one sample should be timed to fall within a window of 8 to 12 hours following a dose of etravirine. (See Section 9.36 for additional information).
21. If a subject is experiencing virologic failure (as defined in section 6.3), a visit to confirm failure must be conducted between 1 to 4 weeks of the initial suspected failure or rebound.
22. At virologic failure, one sample may be collected at any time following a dose of etravirine.

For insufficient blood draws, priorities are as follows:

Hematology (1mL); Chemistry (2mL); Pharmacology (intensive [7mL] or population [1mL]); Virology (HIV-1 RNA PCR – 3mL); Resistance testing (HIV genotype and phenotype – 4mL); Lymphocyte subsets (2mL); CYP genotyping (2mL); Cholesterol / triglycerides (2mL); Coagulation assays (2mL); Plasma/cell pellet for storage (2mL)

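### Section 9.33 on missed doses before the intensive PK visit conflicts with the Appendix I footnotes on timing and with Sections 6.8, 6.9 and 9.35 on leaving the study

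*Protocol*

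**What the plan says.** Section 9.33 of the protocol asks for 7 days of complete dosing before the intensive PK visit on Day 14 (± 4 days). After a miss, "the intensive PK visit should be rescheduled to occur 7- 14 days after the last missed dose". The family is called again the day before the new visit, and a miss in those previous 7 days has this consequence: "If the subject has missed a dose, the PK visit will be cancelled, and the subject will be withdrawn from the study".

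Other places deal with the same child or a similar one:

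- **Appendix IA footnote 16, IB footnote 16, IC footnote 18.** "If the subject has missed a dose, the PK visit must be re-scheduled within the Day 14" (± 4 days) window. There is no withdrawal rule.
- **Section 6.8.** Non-adherence is a criterion for stopping etravirine. A child taken off drug in the first 48 weeks has 4 weeks of safety follow-up under Appendix ID.
- **Section 6.9.** Non-compliance ends study participation only if it harms the child or seriously compromises the validity of the results.
- **Section 9.35.** Suspected non-adherence is referred to 6.6 and 6.8. A child who needs a dose adjustment but refuses the repeat intensive PK stays on study, off drug (3.4 says the same).
- **Section 6.6 (3.3 is similar).** Where a PK result was obtained, is extremely low, and non-adherence is strongly suspected: "The non-adherent subject may remain on study and on study drug (ETR) but will not be considered for dose-finding or safety final analysis".
- **Section 8.1.** If the team judges a child's PK data unevaluable, "the subject will be replaced for dose finding purposes", and this covers the safety criteria as well as the PK criteria.

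**The concern.** A site facing a missed dose needs one answer to two questions: when the new PK visit takes place, and what happens if it cannot be done. The protocol gives more than one answer to each.

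On timing, some missed doses leave no date that satisfies both rules, so the site must deviate from one of them.

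On outcome, leaving the study is a larger step than leaving the drug. Appendix ID is a schedule for children who are off drug but still on study. If a child is withdrawn from the study, the 4-week visit after the last dose may not happen. Nothing further is then collected for the secondary safety analysis in Section 8.1, which takes in all safety data from first exposure onward. If 9.33 meant only stopping the drug, the sentence says something else, and sites cannot tell whether Appendix ID applies.

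**Working it through.** No figure in the documents depends on this rule, so there is none to reproduce. The check has four parts.

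**1. Timing.** If the last missed dose is on Day m, 9.33 allows Day m + 7 to Day m + 14. The footnotes allow Day 10 to Day 18. Both can be met only if m + 7 ≤ 18, that is, m ≤ 11.

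| Last miss | 9.33 | Overlap with Day 10–18 |
|---|---|---|
| Day 7 | 14–21 | 14–18 |
| Day 9 | 16–23 | 16–18 |
| Day 11 | 18–25 | 18 only |
| Day 12 | 19–26 | none |
| Day 13 | 20–27 | none |

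For a visit planned on Day 14, the look-back covers Days 7–13, so misses on Days 12 and 13 fall in the gap. The footnotes also ask for 7 complete days before the visit, and Day 18 is only 6 days after Day 12. For those misses a footnote cannot meet its own two conditions.

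**2. Outcome after a miss in each of two look-back windows.**

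| Place | Trigger | Drug | Study |
|---|---|---|---|
| 9.33 | miss before the rescheduled visit | not stated separately | withdrawn |
| 6.8 | non-adherence | stopped | 4-week follow-up |
| 6.9 | non-compliance with harm or serious effect on validity | – | discontinued |
| 3.4, 9.35 | refuses repeat PK after needing an adjustment | stopped | stays |
| 3.3, 6.6 | very low PK result, non-adherence suspected | may continue | may stay |

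The direct conflict is 9.33 against 6.8, with 6.9 and 9.35 pointing the same way as 6.8. Sections 3.3 and 6.6 have a different trigger, so they show uneven consequences rather than a contradiction.

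**3. Analysis sets.**

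- *Primary safety.* Only evaluable children count: 24 or 48 weeks completed, or a drug-related safety failure. A child withdrawn for missed doses is out. The same child kept on study but taken off drug would also be out.
- *Secondary safety (8.1).* Data collected before withdrawal stay in. Later data do not exist.
- *Virology.* The latest last miss before a Day 18 visit is Day 17, and 17 + 14 = Day 31. The SAP's Week 8 window opens on Day 43, so a withdrawn child has no data at Weeks 8, 12, 24 or 48. SAP 6.4 counts missing data and discontinuation as failure. Protocol 8.6321 says missing data may count as failure, and counts a discontinuation for reasons other than an adverse event or death only if the last viral load exceeded 400. Neither document states the denominator. Table 9 goes up to N = 36, the evaluable number.

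**4. Frequency (illustration only).** Let p be the chance of missing any one dose, with 14 doses in 7 days and independent doses. Then P(withdrawn) = [1 − (1 − p)^14]².

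| p (assumed) | one window | both windows | of 50 children |
|---|---|---|---|
| 1% | 13.1% | 1.7% | 0.9 |
| 2% | 24.6% | 6.1% | 3.0 |
| 5% | 51.2% | 26% | 13.1 |

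Section 6.6 reports that "fewer than 50% of children and/or their caretakers reported full adherence to the regimens" but gives no recall period. If it meant 7 days and exactly 50%, the result would be 0.5² = 25%. Clustering of misses within families would raise these shares. For scale, 50 enrolled for 36 evaluable leaves 50 − 36 = 14 losses from all causes.

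**The case against.** The best defence is that 9.33 covers a case the other sections do not: no valid profile could be obtained in two attempts. In a PK-driven dose-finding study, that could be read as the serious threat to validity that 6.9 mentions. This has some force, but 6.9 calls for a judgement while 9.33 is automatic. Section 8.1 also already protects dose finding by replacing a child whose PK is unevaluable, and 9.35 refers non-adherence elsewhere. The defence does not touch the timing conflict.

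Several stronger readings are tempting, and the documents do not support them:

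- **That 6.6 flatly contradicts 9.33.** Its trigger is a PK result that was obtained, and it too removes the child from the final safety analysis.
- **That withdrawal erases the child's safety data.** Section 8.1 keeps what was collected, and the loss is of later data. Exclusion from the primary safety set would follow from the evaluable definition anyway.
- **That the remaining cohort is selected for near-perfect adherence.** The rule asks for one complete 7-day window in two attempts, early in the trial. Two misses in the same window count once.
- **That antiviral activity is biased upward.** Under SAP 6.4 a withdrawn child kept in the denominator is a failure, which lowers the success rate.

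The frequencies are also open to challenge. The 6-hour allowance for late doses (5.21), the exclusion for past non-adherence (4.29) and the reminder call should all reduce missed doses.

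**Conclusion.** The conflict is real and concerns consistency. No date satisfies both timing rules when the last missed dose is on Day 12 or later; this follows from the stated windows without further assumption. On outcome, 9.33 removes the child from the study where 6.8 stops the drug and keeps 4 weeks of follow-up, and neither 6.9 nor 9.35 supports automatic removal.

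The statistical consequence is limited. A withdrawn child may lose the post-drug safety visit and any later contribution to the all-exposure secondary safety analysis. A reader might infer a distorted virologic result, but its direction depends on a denominator that neither document states. Selection on adherence would arise only if that analysis is limited to evaluable children, which Table 9 suggests but does not say.

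The number affected is unknown. The range of 1.7% to 26% rests entirely on assumed, independent miss rates of 1% to 5% and is not a forecast.

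**What to change.** Reconcile 9.33 with 6.6, 6.8, 6.9, 9.35 and the footnotes to Appendices IA, IB and IC, so that one rule covers both the timing of the rescheduled visit and the outcome if it cannot be done. Which clinical rule to keep is for the protocol team. The reconciled text should say whether the child leaves the drug or the study, and whether Appendix ID follow-up applies.

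Then state the analysis handling in the protocol and SAP:

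- A child with no valid intensive PK is PK-unevaluable and is replaced for dose finding under 8.1, including when the visit was cancelled and no PK data exist.
- Data already collected stay in the all-exposure secondary safety analysis. The primary safety set keeps its evaluable definition.
- The virologic denominator is named, with whether such a child is in it and how the child is classified. The protocol and SAP should agree on this.

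The cost is wording in 9.33, the three footnotes and the cross-referenced sections, plus a short SAP addition. The analysis statements add no visits or samples.
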